### **3.2.3.2. Nonclinical Studies**

A comprehensive series of nonclinical studies were conducted to support the clinical development of ALKS 8700 and are described in more detail in the ALKS 8700 Investigator's Brochure.

Results from genetic toxicity assays showed that ALKS 8700 was non-mutagenic in bacteria *in vitro* and was associated with chromosomal aberrations *in vitro* in human peripheral blood lymphocytes but not *in vivo* in rats. ALKS 8700 had limited capacity to inhibit human ether-à-go-go-related gene (hERG) potassium channel activity in a human cell line (i.e., concentration resulting in 50% inhibition of response [ $IC_{50}$ ] > 300  $\mu$ M). Inhibition of hERG current has been associated with increased duration of the cardiac action potential and prolongation of the QT interval.

General toxicology findings were generally similar to those described for DMF and consisted of target organ effects in kidney (tubular degeneration/necrosis with regeneration, tubular hypertrophy, and interstitial fibrosis in rats, mice, and/or monkeys), GI tract (mucosal hyperplasia of the nonglandular stomach and duodenum of rats and/or mice), bone (physeal dysplasia of proximal and distal femur and proximal tibia in monkeys), heart (inflammation/necrosis in rats), and testes (minimal degeneration in mice).

ALKS 8700 was evaluated for developmental and reproductive toxicity in rats and rabbits. In fertility studies in male and female rats, no notable fertility or embryonic developmental findings occurred. In embryo-fetal development studies in rats and rabbits, noteworthy findings of fetal vertebral malformations were observed in rabbits but not in rats.

The safety evaluation of ALKS 8700 and its metabolites (i.e., MMF, RDC-6567, and RDC-8439) was adequate as systemic exposures of these analytes in nonclinical studies were similar to or exceeded those in humans at the Phase 3 clinical dose of 924 mg/day (462 mg BID) of ALKS 8700. For the major human metabolites, MMF and RDC-6567, the exposures associated with adverse findings in nonclinical safety studies are detailed in the ALKS 8700 Investigator's Brochure.

Data generated through additional nonclinical studies will continue to be evaluated as they become available, including any potential influence on the risk-benefit profile of ALKS 8700.

CONFIDENTIAL

The information contained herein may not be used, disclosed, or published without the written consent of Biogen MA Inc.

See the Investigator's Brochure for further detailed information on relevant nonclinical and clinical studies

### 3.3. Benefit-Risk Assessment

The potential risks related to participation in this study are justified by the anticipated benefit to subjects.

Detailed information about the known and expected benefits and risks and reasonably expected adverse events (AEs) of ALKS 800 is provided in the Investigator's Brochure and informed consent form (ICF). A high-level summary of those benefits and risks known during study design is provided here.

ALKS 8700 is being developed as a modified-release oral treatment for relapsing forms of MS. ALKS 8700 is an aminoethyl ester of MMF that undergoes hydrolysis through esterases to produce MMF. MMF is also the active metabolite of the approved drug product, DMF. An oral form of DMF has been approved by the US Food and Drug Administration since 2013 under the trade name Tecfidera® for the treatment of patients with relapsing forms of MS [Tecfidera® Prescribing Information 2017/SmPC 2017].

In clinical trials, DMF and, by extrapolation, its metabolite, MMF, have demonstrated robust efficacy in modulating the course of disease in patients with RRMS. Compared with placebo, DMF treatment resulted in significant reductions in annualized relapse rate (ARR), disability progression, as well as the number of new gadolinium-enhancing (GdE) lesions and new or enlarging T2 lesions [Fox 2012; Gold 2012; Kappos 2008].

The safety profile of DMF is well understood and GI-related tolerability is a recognized tolerability concern. As noted in the Summary Review of the Drug Approval Package for Tecfidera, in placebo-controlled trials of Tecfidera, 40% of DMF-treated subjects experienced one or more GI AEs. Reviewers described "a panoply of uncomfortable and fairly common GI AEs" that are an "obstacle to tolerability," including nausea, vomiting, diarrhea, and abdominal pain [FDA 2013]. In addition, GI AEs were the leading cause of discontinuations due to AEs [FDA 2013]. The frequency and severity of the GI-related side effects are an important issue for patients taking DMF and is a barrier to treatment adherence and can lead to drug discontinuation which increases risk of relapse [Phillips 2014; Utz 2014]. This underscores the need for an efficacious agent with improved tolerability to optimize patient satisfaction and treatment outcomes [Phillips and Fox 2013].

The ALKS 8700 drug product is a modified-release oral dosage form that provides an MMF exposure profile that may limit GI effects associated with DMF treatment while maintaining efficacy comparable to that demonstrated with DMF. Accordingly, ALKS 8700 has the potential to address an unmet medical need for patients with relapsing forms of MS who are unable to tolerate DMF, particularly due to GI effects.

CONFIDENTIAL

The information contained herein may not be used, disclosed, or published without the written consent of Biogen MA Inc.

#### 4. STUDY OBJECTIVES AND ENDPOINTS

Objective	Endpoints
To evaluate the long-term safety and tolerability of ALKS 8700 for up to 96 weeks of treatment in adult subjects with RRMS	AEs, vital signs, electrocardiogram (ECG) parameters, Columbia Suicide Severity Rating Scale (C-SSRS), and clinical laboratory parameters
To evaluate treatment effect over time in adult subjects with RRMS treated with ALKS 8700	Clinical: ARR, proportion of subjects experiencing MS relapse, progression of disability on the Expanded Disability Status Scale (EDSS), Timed 25-Foot Walk Test (T25-FW), EuroQol Group health outcome measure (5 level; EQ-5D-5L), and 12-item Short Form Health Survey (SF-12)  Exploratory: [REDACTED]

CONFIDENTIAL

The information contained herein may not be used, disclosed, or published without the written consent of  
Biogen MA Inc.

## 5. STUDY DESIGN

### 5.1. Study Overview

This multicenter, open-label study will evaluate the long-term safety and tolerability of ALKS 8700 up to 96 weeks in approximately 1000 subjects. The target population for this study will be adults, aged 18 to 65 years, diagnosed with RRMS. The study will be conducted at approximately 125 sites in North America and Europe.

See [Figure 1](#) for a schematic of the study design.

### 5.2. Study Duration for Subjects

Subjects will enter into the study in one of two ways:

De Novo Subjects: Those who have not participated in any prior eligible study of ALKS 8700.

Rollover Subjects: Those who have completed the treatment period for any prior eligible study of ALKS 8700.

For De Novo Subjects, the study duration is expected to be up to 102 weeks, which includes up to 4 weeks for screening, a 96-week open-label treatment period, and a 2-week follow-up period.

De Novo Subjects will be initially evaluated for eligibility at screening (Visit 1) that may last up to 28 days (4 weeks) prior to Visit 2. For Rollover Subjects, Visit 2 will be the first visit of the study and there will not be a separate screening visit. For these subjects, Visit 2 of this study will occur at the time of or within 7 days of the subject's end of treatment visit in the antecedent study. Completed assessments taken at the end of treatment visit of the antecedent study will be carried forward and do not need to be repeated at Visit 2 of this study unless otherwise specified in the schedule of assessments. At Visit 2, all eligible, consenting subjects will begin open-label treatment. Any subject not currently receiving ALKS 8700 or DMF will initiate treatment with ALKS 8700 231 mg BID on Day 1 through Day 7 followed by 462 mg BID from Day 8 onwards. For those subjects already receiving ALKS 8700 or DMF prior to Day 1, the initial ALKS 8700 dose will be 462 mg BID starting from Day 1.

Dosing is described in detail in [Section 7.1](#). From Day 8 onwards, all participating subjects will take ALKS 8700 462 mg BID, with allowable dose reduction for tolerability as described in [Section 7.2](#).

Study staff will administer the first dose of ALKS 8700 at Visit 2 (Day 1). From that point on during the treatment period, according to the schedule of assessments as shown in [Table 1](#), the staff will dispense ALKS 8700 for subjects' self-administration. Subjects will be instructed to take study treatment with or without food. However, subjects will be instructed to avoid taking study treatment with a high-fat, high-calorie meal.

CONFIDENTIAL

The information contained herein may not be used, disclosed, or published without the written consent of Biogen MA Inc.

During the 96-week treatment period (Visits 2-15), subjects will return to the clinic for periodic scheduled visits for the assessment of safety, tolerability, PK (in a subset of de novo subjects in selected sites), and clinical status. Two safety and tolerability assessments by phone will be scheduled (one between Visits 2 and 3 and one between Visits 3 and 4). See [Figure 1](#) for a study schematic.

Subjects will return to the clinic for a safety follow-up visit (Visit 16) 2 weeks after the end of treatment visit (Visit 15). Any subject who prematurely discontinues from either study treatment or the study will be asked to return to the clinic for an early termination (ET) visit (Visit 15) as well as a safety follow-up visit 2 weeks later (Visit 16).

Subjects who complete the study or who terminate the study early and have a last measured lymphocyte count  $< 0.8 \times 10^3/\mu\text{L}$  will return to the clinic for additional lymphocyte count monitoring visits every 2 months starting from Visit 16 for a period of 6 months (i.e., a maximum of 3 visits) or until lymphocyte counts reach normal limits ( $\geq 0.91 \times 10^3/\mu\text{L}$ ), whichever occurs first.

A treatment completer will be a subject who completes the 96-week treatment period (i.e., through Visit 15). Subjects completing the follow-up visit will be categorized as completing the study.

The end of study date for a subject may be the last study visit, last follow-up telephone conversation, or last protocol-specified assessment, or if the subject has ongoing AEs that are being followed, the date may be the date of AE resolution.

### **5.3. Study treatment Dose Adjustment and Stopping Rules**

Starting on Day 8 of treatment, dose reduction to ALKS 8700 231 mg BID is permitted at the Investigator's discretion for subjects who are unable to tolerate ALKS 8700 462 mg BID. Once a subject has stabilized after dose reduction, attempts should again be made to achieve and maintain the target maintenance dose of ALKS 8700 462 mg BID. If a subject remains unable to tolerate ALKS 8700 462 mg BID after 1 month on treatment (i.e., by Visit 4), further dose reduction will not be permitted, and the subject will be discontinued from the study.

The Sponsor may terminate this study at any time, after informing Investigators. The Sponsor will notify Investigators when the study is to be placed on hold, completed, or terminated.

### **5.4. Unscheduled Visits**

Data collected during unscheduled visits should be recorded in electronic case report forms (eCRFs) only if the data support protocol objectives and/or are required for safety monitoring.

CONFIDENTIAL

The information contained herein may not be used, disclosed, or published without the written consent of Biogen MA Inc.

An Unscheduled Relapse Visit will be conducted in the event of a suspected relapse (Section 7.2.2). This visit should occur as early as possible but within 7 days of the onset of the potential relapse. The following assessments will be made:

- Physical examination
- Concomitant medication review
- AE monitoring
- Urine pregnancy test
- Vital signs
- Safety laboratory assessments
- Relapse assessment
- EDSS

## 5.5. Follow-up

Subjects will return to the clinic for a safety follow-up visit (Visit 16) 2 weeks after the end of treatment visit (Visit 15) for the required assessments (Table 1). Any subject who prematurely discontinues from the study will be asked to return to the clinic for an ET visit (Visit 15) as well as a safety follow-up visit 2 weeks later (Visit 16) for the required assessments (Table 1).

Subjects who complete the study or who terminate the study early and have a last measured lymphocyte count  $< 0.8 \times 10^3/\mu\text{L}$  at the last study visit (Visit 16) will be required to return to the clinic for additional lymphocyte count monitoring visits every 2 months ( $\pm 7$  days) starting from the last study visit for a period of 6 months (i.e., a maximum of 3 visits) or until lymphocyte counts reach normal limits ( $\geq 0.91 \times 10^3/\mu\text{L}$ ), whichever occurs first (Table 2).

During the lymphocyte count monitoring visits, blood samples will be collected to measure lymphocyte count and any concomitant medications the subjects are taking will be recorded (Section 7.7).

## 5.6. End of Study

The end of study is last subject, last visit for final collection of data.

CONFIDENTIAL

The information contained herein may not be used, disclosed, or published without the written consent of Biogen MA Inc.

## 6. STUDY POPULATION

### 6.1. Inclusion Criteria

To be eligible to participate in this study, candidates must meet the following eligibility criteria as listed in [Table 1](#) or at the timepoint specified in the individual eligibility criterion listed.

#### 6.1.1. Rollover Subjects

In order to qualify for participation in this study, Rollover Subjects must meet all of the following criteria:

1. Is willing and able to provide informed consent.
2. Capable of understanding and complying with the protocol.
3. Agrees to use an acceptable method of contraception for the duration of the study and for 30 days after any study treatment administration or is surgically sterile or postmenopausal (see [Section 11.5](#)).
4. Completed the full treatment period of any eligible study of ALKS 8700 within 7 days of Visit 2.

#### 6.1.2. De Novo Subjects

In order to qualify for participation in this study, De Novo Subjects must meet all of the following criteria:

1. Is willing and able to provide informed consent.
2. Capable of understanding and complying with the protocol.
3. Agrees to use an acceptable method of contraception for the duration of the study and for 30 days after any study treatment administration or is surgically sterile or postmenopausal (see [Section 11.5](#)).
4. Male and female adults aged 18 to 65 years, inclusive, at screening.
5. Has a confirmed diagnosis of RRMS according to the revised 2010 McDonald criteria [[Polman 2011](#)].
6. EDSS score of 0.0-6.0 at screening and Visit 2.
7. Neurologically stable with no evidence of relapse within 30 days prior to Visit 2.

CONFIDENTIAL

The information contained herein may not be used, disclosed, or published without the written consent of Biogen MA Inc.

## **6.2. Exclusion Criteria**

### **6.2.1. Rollover Subjects**

Rollover Subjects will be excluded from participation in this trial if they meet any of the following criteria:

1. Have any finding(s) that in the view of the Investigator or Medical Monitor would compromise the safety of the subject, affect their ability to adhere to the protocol visit schedule, or to fulfill visit requirements or make the subject unsuitable for participation in the study (including overall clinical assessment).
2. Subject is pregnant or breastfeeding or plans to become pregnant or begin breastfeeding at any point during the study and for 30 days after any study treatment administration.
3. Is employed by Biogen, contract research organization (CRO), or study site (permanent, temporary contract worker, or designee responsible for the conduct of the study) or is immediate family of a Biogen, CRO, or study site employee. Immediate family is defined as a spouse, parent, sibling, or child, whether biological or legally adopted.

### **6.2.2. De Novo Subjects**

De Novo Subjects will be excluded from participation in this trial if they meet any of the following criteria:

1. Have any finding that in the view of the Investigator or the Medical Monitor would compromise the safety of the subject or affect their ability to adhere to the protocol visit schedule or fulfill visit requirements or make the subject unsuitable for participation in the study (including overall clinical assessment).
2. Diagnosis of primary progressive, secondary progressive, or progressive relapsing MS as defined by Lublin and Reingold [\[Lublin and Reingold 1996\]](#).
3. History of clinically significant cardiovascular, pulmonary, GI (e.g., inflammatory bowel disease, peptic ulcer disease), dermatologic, psychiatric, neurologic (other than MS), endocrine, renal and/or other major disease that would preclude participation in a clinical trial.
4. History of clinically significant recurring or active GI symptoms (e.g., nausea, diarrhea, dyspepsia, constipation) within 3 months of screening, including symptoms that require the initiation of symptomatic medical treatment (e.g., initiation of a medication to treat gastroesophageal reflux disease) or a change in symptomatic medical treatment (e.g., an increase in dose) within 3 months of screening.
5. History of malignancy, unless an exception is granted by the Medical Monitor (e.g., subjects with basal cell carcinoma that has been completely excised prior to study entry remain eligible).

CONFIDENTIAL

The information contained herein may not be used, disclosed, or published without the written consent of  
Biogen MA Inc.

6. Has a clinically significant medical condition or observed abnormality at screening (e.g., clinically significant physical examination finding, vital sign result, ECG result, or laboratory test result).
7. History of a myocardial infarction, including a silent myocardial infarction identified on ECG, or unstable angina.
8. History of clinically significant drug or alcohol abuse within the past year (per Investigator judgment).
9. Has a positive serology test for hepatitis B surface antigen, hepatitis C antibody, or human immunodeficiency virus (HIV) antibody at screening.
10. Has any of the following abnormal blood tests at screening:
  - Alanine aminotransferase (ALT) or aspartate aminotransferase (AST)  $\geq$  2 times the upper limit of normal (ULN)
  - Thyroid-stimulating hormone (TSH) level  $>10\%$  of the ULN at screening
  - Estimated glomerular filtration rate (eGFR)  $\leq$  60 mL/min/1.73 m^2 (using the Chronic Kidney Disease Epidemiology Collaboration equation) [\[Levey 2009\]](#)
  - Lymphocyte count  $< 0.9 \times 10^3/\mu\text{L}$
11. Has any of the following abnormal urine tests at screening:
  - Beta-2 microglobulin  $> 0.3 \mu\text{g/mL}$
  - Albumin to creatinine ratio  $> 200 \text{ mg/g}$
12. Has a clinically significant history of suicidal ideation or suicidal behavior occurring in the past 12 months as assessed by the C-SSRS at screening.
13. Has previously discontinued treatment with Tecfidera due to tolerability issues and/or lack of efficacy.
14. Has a history of treatment with or has received the following:
  - Total lymphoid irradiation, cladribine, T-cell or T-cell receptor vaccination, total body irradiation, or total lymphoid irradiation at any time
  - Stem cell transplantation at any time
  - Mitoxantrone or other immunosuppressant agents (e.g., cyclosporine, cyclophosphamide, methotrexate, mycophenolate) within 2 years prior to Visit 2

CONFIDENTIAL

The information contained herein may not be used, disclosed, or published without the written consent of Biogen MA Inc.

- Teriflunomide within 2 years of Visit 2, unless the serum/plasma concentration of teriflunomide is < 0.020 µg/mL (< 20 ng/mL) prior to Visit 2 (an accelerated elimination procedure for teriflunomide with cholestyramine is permitted during screening)
- Natalizumab within 2 months prior to Visit 2 or any prior use of alemtuzumab
- Fingolimod within 90 days prior to Visit 2
- Daclizumab within 6 months prior to Visit 2
- B-cell targeted therapies for the treatment of MS (e.g., ocrelizumab, rituximab) within 12 months of screening; greater than 12 months of screening is permissible with evidence that the CD19 cells have returned to within normal range (per local laboratory reference range)
- Eligibility related to prior treatment with an investigational drug and/or a commercially available drug for the treatment of MS not listed above within the past 24 months will be determined on a case-by-case basis by the Medical Monitor
- Steroids, with the exception of topical or inhaled steroids, or intravenous (IV) immunoglobulin within 30 days prior to Visit 2

15. Current or prior participation in a clinical trial within 3 months of screening.

16. Subject is pregnant or breastfeeding or plans to become pregnant or begin breastfeeding at any point during the study and for 30 days after any study treatment administration.

17. Is employed by Biogen, CRO, or study site (permanent, temporary contract worker, or designee responsible for the conduct of the study) or is immediate family of a Biogen, CRO, or study site employee. Immediate family is defined as a spouse, parent, sibling, or child, whether biological or legally adopted.

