**Table 3: Clinical Laboratory Assessments**

Hematology 	Biochemistry	Urinalysis
Hematocrit	Sodium	Color
Hemoglobin	Potassium	pH
Red blood cell count	Chloride	Specific gravity
Total and differential (absolute) white blood cell count	Bicarbonate	Ketones
Platelets	Glucose	Protein
	Thyroid-stimulating hormone (TSH) 	Glucose
	Calcium	Bilirubin
	Uric Acid	Nitrite
	Creatinine	Urobilinogen
	Total protein	Occult blood
	Blood urea nitrogen	Microscopic examination of sediment only if urinalysis dipstick results are abnormal
	Albumin	Urine albumin
	Total bilirubin	Urine beta-2-microglobulin
	Alanine aminotransferase (ALT)	Urine creatinine
	Aspartate aminotransferase (AST)	
	Lactic dehydrogenase (LDH)	
	Alkaline phosphatase	
	Creatine phosphokinase	
	Lipid profile: blood cholesterol, high-density lipoprotein, low density lipoprotein, and triglycerides	

 Additional hematology assessments will be collected for subjects requiring follow-up for lymphopenia at the time of study completion or early termination.

 To be assessed at screening only.

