## **12.8. Sample Size Considerations**

No formal sample size calculation is performed for this study. A sample size of approximately 1000 subjects will contribute to the long-term safety experience of ALKS 8700 in subjects with RRMS, taking into account International Council for Harmonisation (ICH) guidance on the extent of patient exposures required to assess clinical safety for a new drug.

CONFIDENTIAL

The information contained herein may not be used, disclosed, or published without the written consent of  
Biogen MA Inc.

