	Platelets	$< 75.1 \times 10^3/\mu\text{L}$ $\geq 700 \times 10^3/\mu\text{L}$
	WBCs - total, differential (absolute)	$\leq 2.8 \times 10^3/\mu\text{L}$ $\geq 16 \times 10^3/\mu\text{L}$
	lymphocytes	$< 0.5 \times 10^9/\text{L}$
	Eosinophils	$> 1.0 \times 10^3 \text{ cells}/\mu\text{L}$
Chemistry	ALT	$\geq 3 \times \text{ULN}$
	Albumin	< 2.5 g/dL
	ALK-P	$\geq 3 \times \text{ULN}$
	AST	$\geq 3 \times \text{ULN}$
	Bicarbonate	< 15 mmol/L > 31 mmol/L
	BUN	> 30 mg/dL

Category	Parameter	Criteria
	Calcium	< 8.2 mg/dL > 12 mg/dL
	Chloride	\leq 90 mmol/L \geq 118 mmol/L
	Creatine Kinase	$> 3 \times$ ULN
	Creatinine	\geq 2 mg/dL
	Gamma Glutamyltransferase	$\geq 3 \times$ ULN
	Glucose	< 50 mg/dL > 200 mg/dL
	HDL Cholesterol	\leq 30 mg/dL
	Lactate Dehydrogenase	$> 3 \times$ ULN
	LDL Cholesterol	\geq 160 mg/dL
	Phosphate	< 2 mg/dL > 5 mg/dL
	Potassium	< 3 mmol/L > 5.5 mmol/L
	Prolactin	$> 1 \times$ ULN
	Sodium	< 130 mmol/L > 150 mmol/L
	Thyroid stimulating hormone (TSH)	$> 5.5 \mu\text{IU}/\text{mL}$
	Total Bilirubin	\geq 2 mg/dL
	Total Cholesterol	$> 300 \text{ mg/dL}$
	Triglycerides	$\geq 120 \text{ mg/dL}$ (Female) $\geq 160 \text{ mg/dL}$ (Male)
	Uric Acid	$> 9 \text{ mg/dL}$ $> 8 \text{ mg/dL}$ (Female) $> 10 \text{ mg/dL}$ (Male)
Urinalysis	Glucose	at least 2+
	Protein	at least 2+

For liver function tests, the number and percentage of subjects will be summarized by upper limit of normal (ULN) category as follows:

- ALT (alanine aminotransferase), AST (aspartate aminotransferase) and ALK-P (alkaline phosphatase) will be summarized by normal, $> 3 \times \text{ULN}$, $> 5 \times \text{ULN}$ and $> 10 \times \text{ULN}$.

Number of subjects who meet Hy's Law criteria (total Bilirubin $> 2 \times \text{ULN}$ and ALT or AST $> 3 \times \text{ULN}$) will be summarized and corresponding listing will be presented.

In addition, number of Subjects with Lymphopenia by Maximum NCI-CTCAE Toxicity Grade 1-4 will be summarized. A listing with all post-discontinuation lymphocyte counts from subjects who require additional lymphocyte count monitoring visits, as per the protocol, will also be provided.

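### The De Novo TSH exclusion is printed as a fraction of the ULN, so the threshold is wrong as written and the limit intended appears nowhere in the documents

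*Protocol*

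**What the plan says.** Protocol 6.2.2 opens its list with "De Novo Subjects will be excluded from participation in this trial if they meet any of the following criteria". Criterion 10 has the stem "Has any of the following abnormal blood tests at screening" and four bullets. The first, "Alanine aminotransferase (ALT) or aspartate aminotransferase (AST"), is set at ≥ 2 times the ULN. The second reads "Thyroid-stimulating hormone (TSH) level" >10% "of the ULN at screening". The other two (eGFR and lymphocyte count) are absolute values.

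TSH appears in two other places. Protocol Table 3 lists it under biochemistry with the footnote "To be assessed at screening only". SAP 3.6.5, Table 2, has a row "Thyroid stimulating hormone (TSH") with a potentially clinically significant (PCS) limit of > 5.5 µIU/mL. Neither restates the eligibility limit. The amendment summaries, as supplied, do not mention TSH. The Rollover exclusions in Protocol 6.2.1 contain no TSH item.

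SAP 3.1.3 summarises major protocol deviations by enrollment group, and failure to meet eligibility criteria is one of its categories.

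**The concern.** A percentage of the ULN is not the same as a percentage above it. As printed, the criterion treats a TSH of one tenth of the ULN as the boundary, and most values that a laboratory would report as normal lie above that. A site cannot sensibly apply the text as it stands and has to choose a meaning.

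Two things are at stake. First, the rule that actually decided De Novo entry on TSH may be one that neither document contains, and it may differ between sites. Second, if the deviation category in SAP 3.1.3 were derived from the printed wording, it could flag most De Novo Subjects and none of the Rollover Subjects, and so distort one of the three enrollment groups that the SAP reports.

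**Working it through.** The plan gives no figure to reproduce: there is no reference range and no expected screen-failure rate, and Protocol 12.8 states "No formal sample size calculation is performed for this study". The check has three steps.

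**Step 1: the literal limit, by arithmetic alone.** Limit = 0.10 × ULN. Any TSH with 0.10 × ULN < TSH ≤ 1.00 × ULN meets the exclusion without exceeding the ULN. The neighbouring ALT/AST bullet starts at 2 × ULN, so the multiplier on the ULN is 20 times larger there (2 / 0.10). For illustration, assumed ULNs of 4.0, 4.5, 5.0 and 5.5 µIU/mL give literal limits of 0.40, 0.45, 0.50 and 0.55 µIU/mL.

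**Step 2: the share of candidates caught by the literal limit.** This needs assumptions that the documents do not supply:

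- TSH is log-normal among candidates.
- The reference interval from LLN to ULN is the central 95%.
- r = LLN/ULN lies between 0.03 and 0.20.

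With TSH expressed in units of the ULN:

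- sd of ln(TSH) = ln(1/r) / (2 × 1.96)
- P(TSH > c × ULN) = 1 − Φ((ln c + 1.96 × sd) / sd)

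Worked case, r = 0.03: sd = 3.507 / 3.92 = 0.895. With c = 0.1, (−2.303 + 1.753) / 0.895 = −0.61, so P = 0.73.

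| r = LLN/ULN | sd | Excluded at 0.10 × ULN | Share of those with normal TSH who are excluded | Excluded at 1.10 × ULN |
|---|---|---|---|---|
| 0.03 | 0.895 | 73.0% | 74% | 1.94% |
| 0.05 | 0.764 | 85.4% | 87% | 1.85% |
| 0.07 | 0.678 | 92.4% | 95% | 1.78% |
| 0.10 | 0.587 | 97.5% | 100% | 1.69% |
| 0.15 | 0.484 | 99.7% | 100% | 1.55% |
| 0.20 | 0.411 | >99.9% | 100% | 1.42% |

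When r is below 0.10, the literal limit lies inside the reference interval. When r is 0.10 or more, it lies at or below the LLN, and every normal value above it is excluded.

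**Step 3: the gap between two plausible intended readings.** Above the ULN (c = 1.0) excludes 2.5% by construction. More than 10% above the ULN (c = 1.1) excludes 1.42% to 1.94%. The difference is 2.5 − 1.94 = 0.6 to 2.5 − 1.42 = 1.1 percentage points of De Novo candidates.

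**The case against.** The strongest reply is that the bullet should be read with its stem. A TSH inside the reference range is not an abnormal test, so no sensible site would exclude someone for it, and the large percentages measure a reading that was probably never used. This stands as far as it goes: literal application is unlikely. But the stem supplies no number. It tells a site that the printed limit cannot be meant, without saying what is.

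A second reply is that little hangs on it. This also largely stands. The safety, FAS and PK sets in SAP 3.1.1 are not conditional on eligibility, and there is no per-protocol set. TSH is measured at screening only, and only De Novo Subjects are affected. Criteria 3 and 6 separately cover clinically significant endocrine disease and clinically significant screening laboratory results. They rely on judgment, however, and do not replace a numeric exclusion.

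Several stronger inferences are tempting but not supported:

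- **That the criterion shuts out almost every De Novo candidate.** This needs a literal application that the stem makes improbable. Even then the modelled share falls to 73% at the low end of the assumed range.
- **That the limit lies inside the normal range.** This is true only if the LLN is below 0.10 × ULN, and no reference range is given.
- **That the SAP's 5.5 µIU/mL is the ULN.** It is a PCS limit, and other limits in the same table are set at 3 times the ULN.
- **That the SAP 3.1.3 count is wrong.** The SAP does not say that eligibility deviations are derived from TSH values. SAP 3.8 refers to a protocol deviations log, and the dataset and programming specifications are separate documents. The count could be affected; it is not shown to be.

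**Conclusion.** Wrong as written, and minor. That the printed limit conflicts with its own stem follows from the text and needs no outside figure. The share it would exclude if taken literally, about 73% to over 99.9%, rests on the log-normal model and the assumed LLN/ULN range, and it describes a reading that was probably not applied.

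The practical defect is narrower: De Novo eligibility on TSH was decided by a limit that neither document states. Between the two readings considered, the difference is about 0.6 to 1.1 percentage points of De Novo candidates under the same model. The eligibility-deviation count for De Novo Subjects could be distorted if it is taken from the printed text. No analysis set depends on the criterion.

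**What to change.** The sponsor should reconcile the TSH bullet with the stem of criterion 10 and with what the central laboratory and sites actually applied. It should then restate the limit so that it can be read only one way relative to the ULN. The same rule should be used when eligibility deviations are identified for SAP 3.1.3. Which value was intended is for the sponsor to say; none is proposed here.

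The cost is one line in an amendment or clarification letter. If De Novo enrolment has closed, a note recording the rule that was applied, cited in the deviation specification, is enough. There is a precedent: an earlier amendment reworded the De Novo albumin-to-creatinine limit from 0.2 mg/mg to 200 mg/g to match laboratory reports, although the two are the same quantity (0.2 × 1000 = 200).
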